5.2 Subject Exclusion Criteria

All must be answered NO for the subject to be eligible for study participation:

- 1) History of a chronic medical or surgical condition that would interfere with the accurate assessment of the trial's objectives or increase the subject's risk profile
 - *Note: Chronic medical conditions include: diabetes mellitus; asthma requiring use of medication in the year before screening; autoimmune disorder such as lupus erythematosus, Wegener's, rheumatoid arthritis, thyroid disease; cardiovascular disease, including coronary artery disease or cerebrovascular disease, or surgery; syncope related to cardiac arrhythmia or unexplained; chronic hypertension; malignancy except low-grade (squamous and basal cell) skin cancer thought to be cured; chronic renal, hepatic, pulmonary, or endocrine disease, myopathy, or neuropathy; gastrointestinal or biliary surgery.*
- 2) History of hypersensitivity or severe allergic reaction of any type to medications, bee stings, food, or environmental factors
 - *Note: Severe allergic reaction is defined as any of the following: anaphylaxis, urticaria, or angioedema*
- 3) Active allergic symptoms to seasonal and animal allergens that require treatment

-
- 4) A marked baseline prolongation of ECG intervals, or HR <45 bpm or >100 bpm on ECG measurements
 - *Note: The following are considered prolonged ECG intervals: QTc/QTcF >449 msec in males and females; PR >209 msec; and QRS >110 msec*
 - 5) Clinically significant abnormal ECG results
 - *Note: Clinically significant abnormal ECG results include: complete left or right bundle branch block; other ventricular conduction block; 2nd degree or 3rd degree atrioventricular (AV) block; sustained atrial or ventricular arrhythmia; two premature ventricular contractions in a row; pattern of ST elevation felt consistent with cardiac ischemia; evidence of a previous myocardial infarction (MI), left ventricular hypertrophy (LVH), or more than minor non-specific ST-T wave changes; or any condition deemed clinically significant by a study investigator.*
 - 6) Abnormal renal function
 - *Note: Normal renal function is defined as normal creatinine [per criteria in [Appendix B](#)] and normal estimated glomerular filtration rate (eGFR) [i.e., >80.0 mL/min] values according to Cockcroft-Gault.*
 - 7) Positive serology results for HIV, HBsAg, or HCV
 - 8) Febrile illness with temperature >37.6°C for <7 days before dosing

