7.4 Inpatient period (Days 1 to 4)

7.4.1 Administration of Study Drug (Day 1)

A subject will be enrolled in the trial and receive the study drug on Day 1 if he/she continues meeting the eligibility criteria by assessments performed before dosing

Before Dosing:

- Withhold breakfast but allow access to water
- Update MH
- Update Prior Medications
- Obtain VS (within 60 min before dosing)
- Perform symptom-directed PE (if applicable)
- Obtain 12-lead ECG with 10-sec rhythm strip (within 60 min before dosing)
- May insert IV catheter for blood collection into a forearm vein
- Obtain blood (plasma) PK sample (30 min before dosing)

Dosing:

- Administer a single 4-g dose of zoliflodacin orally as a [REDACTED] followed by [REDACTED] chase
- Withhold food until 4 h after dosing but allow access to water

After Dosing:

- Obtain VS at 1 h (± 10 min), 2 h (± 10 min), and 4 h (± 10 min) after dosing; more frequent monitoring will be at the PI's discretion based on subject's clinical presentation
- Perform symptom-directed PE (if applicable)
- Perform AE and SAE assessments
- Obtain 12-lead ECG with 10-sec rhythm strip at 1 h (± 10 min), 2 h (± 10 min), and 4 h (± 10 min) after dosing
- Obtain blood (plasma) PK samples at 0.5 h (± 5 min), 1 h (± 5 min), 2 h (± 5 min), 3 h (± 10 min), 4 h (± 10 min), 6 h (± 10 min), 8 h (± 15 min), and 12 h (± 15 min) after dosing
- Document ConMeds

7.4.2 In-patient Follow-up Day 2

- Update MH
- Obtain VS
- Perform symptom-directed PE (if applicable)
- Perform AE and SAE assessments
- Obtain blood (plasma) PK samples at 24 h (± 2 h) and 36 h (± 2 h) after dosing
- Document ConMeds

7.4.3 In-patient Follow-up Day 3

- Update MH
- Obtain VS
- Perform symptom-directed PE (if applicable)

- Perform AE and SAE assessments
- Obtain blood (plasma) PK samples at 48 h (± 2 h) after dosing
- Document ConMeds

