9.2.3 Serious Adverse Events

An SAE is any AE that meets at least one of the following criteria:

- Death;
- Life-threatening AE*;
- Inpatient hospitalization or prolongation of existing hospitalization;
- Persistent or significant disability or incapacity, or substantial disruption of the ability to conduct normal life function;
- Congenital anomaly/birth defect;
- Important medical events that may not result in death, be life-threatening, or require hospitalization may be considered an SAE when, based upon appropriate medical judgment, they may jeopardize the subject and may require medical or surgical intervention to prevent one of the outcomes listed in this definition. Examples of such medical events include allergic bronchospasm requiring intensive treatment in an emergency room or at home, blood dyscrasias or convulsions that do not result in inpatient hospitalization, or the development of drug dependency or drug abuse.

*Life-threatening AE. An AE is considered “life-threatening” if, in the view of either the investigator or sponsor, its occurrence places the subject at immediate risk of death. It does not include an AE that, had it occurred in a more severe form, might have caused death.

SAEs will be:

- Assessed for severity and relationship to study product and alternate etiology by an authorized study physician (listed on FDA Form 1572);
- Recorded on the appropriate SAE data collection form and eCRF;
- Followed through resolution;
- Reviewed and evaluated by an ISM (as deemed necessary), the SMC (periodic review unless related), DMID, and the IRB.

9.2.4 Procedures to be Followed in the Event of Abnormal Laboratory Test Values or Abnormal Clinical Findings

A licensed study clinician (listed on FDA Form 1572) will make the determination of seriousness, severity, and causality; provide a medical evaluation of AEs; and classify AEs based upon medical judgment.

Abnormal laboratory values or clinical findings for all enrolled subjects, including values and findings noted at screening and baseline, will be assessed using the toxicity scales in [Appendix C](#). Abnormal values and findings noted at screening or baseline will only be considered AEs if

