Note 2: Safety laboratory results that are abnormal according to the local laboratory reference range, but not considered a Grade 1 abnormality, will be evaluated by the study site clinician and reported as Grade 1 abnormality if clinically significant. If not clinically significant, these will not be considered laboratory AEs and will thus not be graded, but will be recorded in the source document and followed-up clinically at the discretion of the study site clinician.

Note 3: Other laboratory parameters performed and reported as part of the complete blood count, metabolic panel and urinalysis will be evaluated by the study physician, recorded in the source document, and reported as laboratory AEs if clinically significant, and graded according to the criteria in [Section 9.2.1](#).

Note 4: If US by dipstick is abnormal, a microscopic UA will be performed and the results will supersede the results of the dipstick UA.

Note 5: Menstruating females with a positive urine dipstick or microscopic UA may be retested following cessation of menses.

| ECG interval abnormality | Grade 1 | Grade 2 | Grade 3 |
|--|---|--|---|
| QT/QTc interval (Fridericia's correction) prolonged (msec) | Asymptomatic, QTc 450-479 msec, OR increase in interval <30 msec above baseline | Asymptomatic, QTc 480-499 msec OR increase in interval 30-59 msec above baseline | Asymptomatic, QTc \geq 500 msec OR increase in interval \geq 60 msec above baseline |
| PR interval prolonged - sec | 0.21-0.25 sec | >0.25 sec | Type II 2 nd degree AV block OR ventricular pause >3.0 sec |

Note: The events will be coded as SAE if there are life-threatening associated symptoms or signs (arrhythmia, CHF, hypotension, syncope, torsade's de pointes, etc.)

Note: If a male subject was accepted into the trial with a QT/QTc value that overlaps with values used for grading Grade 1 (mild) QT/QTc prolongation, an AE will be reported if the on-study value of the QT/QTc is higher than the baseline.

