9.9. Other Safety Measures

A 12-lead ECG and 10-sec rhythm strip will be obtained at Screening Visit and on Days -1, 1, and 4 (72 h \pm 2 h post dose), or ET. On Day 1, a 12-lead ECG and 10-sec rhythm strip will be recorded within 1 h before dosing and 1 h (\pm 10 min), 2 h (\pm 10 min), and 4 h (\pm 10 min) after dosing. ECG change in overall interpretation from baseline will be shown by study visit in [Table 107](#). For PR interval and QT intervals with Fridericia correction (QTcF), ECG results will be tabulated by parameter, severity grading, and visit ([Table 108](#) and [Table 109](#)). Summary statistics of ECG results, including change from baseline, will be reported by parameter (PR interval, QRS duration, QT interval, QTcF interval, RR interval, and ECG mean ventricular rate) in tabular form by study visit ([Table 110](#), [Table 111](#), [Table 112](#), [Table 113](#), [Table 114](#), and [Table 115](#)) and will be shown graphically as line plots by visit ([Figure 33](#), [Figure 34](#), [Figure 35](#), [Figure 36](#), [Figure 37](#), [Figure 38](#), and [Figure 39](#)). Subjects will not be labeled in the line plots, as the purpose of the figures is to give an overall trend of trajectory. Line plots of change from baseline will be shown for QTcF intervals ([Figure 37](#)) but change from baseline will not be shown graphically for other ECG parameters. Frequency of QTcF prolongation (between 30 and <60 msec or \geq 60 msec) will be given by post-dose visit ([Table 116](#)). Individual data listings of ECG results (interpretation, PR interval, QRS duration, QT interval, QTcF interval, RR interval, and ECG mean ventricular rate) will be presented ([Listing 17](#)).

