Max Severity Post Baseline	x	x	x	x	x	x	x	x	x	x	x

Note: The “Max Severity Post Baseline” rows indicate the maximum severity experienced by each subject at any time point post baseline, including unscheduled assessments. N=Number of subjects in the Safety Population.

Table 109: ECG by Parameter, Maximum Severity, and Time Point – QTcF Interval, Aggregate

This table will repeat Table 108 for QTcF Interval, Aggregate.
--

Table 110: ECG Summary Statistics by Parameter and Time Point – PR Interval, Aggregate (msec)

Time Point	N	Mean	Standard Deviation	Median	Min, Max
Baseline					
1 h (± 10 min) after dosing					
1 h, Change from Baseline					
2 h (± 10 min) after dosing					
2 h, Change from Baseline					
4 h (± 10 min) after dosing					
4 h, Change from Baseline					
72 h (± 2 h) after dosing					
72 h, Change from Baseline					

N = number of subjects in the Safety Population with the ECG parameter assessed for the respective time point

Table 111: ECG Summary Statistics by Parameter and Time Point – QRS Duration, Aggregate (msec)

This table will repeat Table 110 for QRS Duration, Aggregate.

Table 112: ECG Summary Statistics by Parameter and Time Point – QT Interval, Aggregate (msec)

This table will repeat Table 110 for QT Interval, Aggregate.

Table 113: ECG Summary Statistics by Parameter and Time Point – QTcF Interval, Aggregate (msec)

This table will repeat Table 110 for QTcF Interval, Aggregate.

Table 114: ECG Summary Statistics by Parameter and Time Point – RR Interval, Aggregate (msec)

This table will repeat Table 110 for RR Interval, Aggregate.

Table 115: ECG Summary Statistics by Parameter and Time Point – ECG Mean Ventricular Rate (msec)

This table will repeat Table 110 for ECG Mean Ventricular Rate.

Table 116: ECG Measurements, Frequency of QTcF Prolongation

Time Point	Prolongation Between 30 and <60 msec		Prolongation ≥60 msec	
	N	n (%)	N	n (%)
1 h Post Dose				
2 h Post Dose				
4 h Post Dose				
72 h Post Dose				

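### QTcF Grade 1 as written includes any rise below 30 msec, so with no drug effect SAP Table 109 would grade about half of subjects per visit and roughly 67–82% on its maximum row

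*Protocol*

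**What the plan says.** - **Grade definition.** The ECG table in Protocol Appendix C gives QTcF Grade 1 as "Asymptomatic, QTc 450-479 msec, OR increase in interval <30 msec above baseline". Grade 2 takes over at a rise of 30 msec and Grade 3 at 60 msec. The ECG block of SAP Table 4 repeats the wording.
- **Use of the grade.** SAP Section 9.9: "For PR interval and QT intervals with Fridericia correction (QTcF), ECG results will be tabulated by parameter, severity grading, and visit". The QTcF display is Table 109, whose shell reads "This table will repeat Table 108 for QTcF Interval, Aggregate". Table 108 has rows for baseline, 1 h, 2 h, 4 h and 72 h, and a maximum row that also counts unscheduled ECGs. Listing 17 prints a severity beside each ECG result.
- **Baseline.** SAP Section 3.3 takes the last value before dosing.
- **Entry limit.** Exclusion criterion 4 (Protocol Section 5.2) treats as prolonged "QTc/QTcF >449 msec in males and females; PR >209 msec; and QRS >110 msec". Under Protocol Section 7.4.1 a subject is dosed only if he or she "continues meeting the eligibility criteria by assessments performed before dosing".
- **Male-subject note.** Below the ECG table, Appendix C has a rule that begins "If a male subject was accepted into the trial with a QT/QTc value that overlaps with values used for grading Grade 1". It makes a higher on-study value reportable as an AE.
- **Clinical-significance filter.** Notes 2 and 3 of Appendix C let the clinician set aside findings that are not clinically significant, but they concern laboratory values. Note 2 opens "Safety laboratory results that are abnormal according to the local laboratory reference range, but not considered a Grade 1 abnormality".

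**The concern.** A grade is meant to separate abnormal readings from ordinary variation. The change limb of QTcF Grade 1 has a ceiling but no floor, so any positive change qualifies, including one within measurement noise. The baseline reading has no change from itself and the entry rule keeps it below 450 msec. The Baseline row will therefore sit almost wholly in the None column, while the post-dose rows can fill the Grade 1 column by chance. A reader of the CSR would see a move to mild QTcF prolongation after a 4-g dose that is being considered for a thorough QTc study, with no control group to show that the move is noise.

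The reach is limited to Table 109 and the severity column of Listing 17. AE tables are touched only if the investigator reports such rises as ECG AEs, because the automatic entry of Grade 1 findings in Protocol Section 9.2.4 covers laboratory values only. The secondary ECG endpoint is change from baseline (Table 113) and is unaffected. So are Table 116, Figure 37 and the Grade 3 halting criterion. Nothing in the documents says that the SMC receives Table 109.

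**Working it through.** The documents give no expected grade rate, QTcF SD or correlation, so there is no planned figure to reproduce.

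**Inputs from the documents.** Eight subjects (SAP Section 5); one baseline reading (SAP Section 3.3); four scheduled post-dose ECGs at 1, 2, 4 and 72 h (SAP Section 3.2); the Grade 1 wording above; entry at QTcF 449 msec or less.

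**1. Per visit, no drug effect.** If baseline and post-dose readings have the same distribution, the change is symmetric about zero. P(change > 0) = 1/2, which is 4 of 8 subjects per visit, whatever the SD.

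**2. Maximum row.** A subject stays ungraded only if no post-dose reading exceeds baseline, that is, if baseline is the largest of five readings. For exchangeable readings P = 1/5, so P(graded) = 1 − 1/5 = 0.80, or 8 × 0.80 = 6.4 subjects. One unscheduled ECG gives 1 − 1/6 = 0.833, or 6.7 subjects. At 0.80 per subject the binomial probability that at least 5 of 8 are graded is 0.94.

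**3. Rounding and correlation.** Simulation of 400,000 subjects per scenario, readings rounded to 1 msec, baselines above 449 msec removed. Assumed: mean QTcF 405 msec, between-subject SD 15, within-subject SD 5 to 15, no shift. Any grade on the maximum row:

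| Correlation of the readings | Graded, maximum row |
|---|---|
| Independent | 77.6–80.3% |
| 0.5 within Day 1, 72 h independent | 79.4–82.1% |
| 0.5 between all five | 76.6–79.5% |
| Serial 0.5 | 74.2–77.1% |
| Serial 0.7 | 71.9–75.1% |
| Serial 0.9 | 67.4–72.0% |

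Per visit these scenarios give 41.1–50.0%; rounding creates ties, which count as no rise. With independent readings, mean 395–415, between-subject SD 12–18 and within-subject SD 6–15, the rates are 47.5–51.6% per visit and 78.0–82.1% on the maximum row. Together: 41–52% and 67–82% (5.4–6.6 of 8).

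**4. Separate check by correlation between the changes.** Numerical integration gives 81.6% at 0.45, 80.0% at 0.5, 72.9% at 0.7, 68.6% at 0.8 and 63.1% at 0.9. A shared Day 1 effect with a separate 72 h effect gives 81–84%. Wider assumptions thus span about 63–84%.

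**5. Composition.** These are rates for any grade. With independent readings, nearly all are Grade 1 at within-subject SD up to 8 msec. At SD 10–15, about 6–23% of subjects reach Grade 2 or higher on the maximum row; at SD 15 about 80% are graded, 58% with Grade 1 as their worst grade.

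**6. Small non-drug drift.** A shift of −5 or +5 msec at SD 6 and 12 moves the maximum row to 45–96% for correlation 0 to 0.5, and to 19–98% for serial correlation 0.9. The row then mostly records the sign of a small drift.

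**7. If rises below 30 msec are left ungraded.** With no shift, the maximum row falls to 0.1–20% at SD 6–12 (at most 1.6 of 8) and 3–31% at SD 15 (at most 2.5 of 8). With the ±5 msec shift at SD 6–12 it is at most 23%.

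**The case against.** The strongest reply is that a narrower rule was intended. The row concerns prolonged intervals, and Protocol Section 9.2.4 applies the scales to "Abnormal laboratory values or clinical findings for all enrolled subjects", not to every reading. The male-subject note would be largely redundant if every rise were already Grade 1. SAP Section 9.9 does not say whether grades are derived by program or assigned by the investigator. This makes another intent plausible. It does not supply one: no floor is written in the ECG row or in Table 109, and requiring QTcF of at least 450 msec for the change limb would leave that limb with nothing to do. The note itself covers men admitted with a Grade 1 QTc, whom exclusion criterion 4 keeps out.

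Second, the 67–82% range rests on assumed SDs and correlations and on no drift. That stands. Only the 50% and 80% results are free of those assumptions, and they need symmetry and exchangeability. It is also fair that a majority is graded on the maximum row only, not at each visit.

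Third, little is at stake: Tables 113 and 116 give a reader the change and the large rises. That stands too, and limits the point to minor.

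Fourth, a display rule that departs from Appendix C might be thought to go too far, and a neutral footnote stating what Grade 1 includes would inform the reader without a second scale. It would, but the table would still be filled mainly by noise.

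**Conclusion.** The concern holds, as a minor one. Applied as written, the Grade 1 change limb makes Table 109 show a shift from baseline that needs no drug effect: 50% of subjects per visit and 80% (6.4 of 8) on the maximum row for exchangeable readings, or 41–52% and roughly 67–82% with rounding over the assumed SDs and correlations. It assumes that Table 109 grades follow the limits in SAP Table 4, the only QTcF scale in the SAP, and that there is no non-drug drift; a drift of 5 msec either way widens the maximum row to 19–98%. There is also an inconsistency that needs no calculation: SAP Section 9.9 counts prolongation from 30 msec in Table 116, while Table 109 would grade it from 1 msec.

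**What to change.** 1. Ask the sponsor to reconcile the Grade 1 change limb and the male-subject note (Appendix C and SAP Table 4) with the 449 msec exclusion limit and the QTcF displays in SAP Section 9.9. Which clinical grading rule is right is for the sponsor to settle.
2. Add this footnote to SAP Table 109 and Listing 17:

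> For these displays, Grade 1 is QTcF 450–479 msec. Change from baseline is graded from 30 msec only (30 to <60 msec Grade 2, ≥60 msec Grade 3, the limits of Table 116). Absolute limits for Grades 2 and 3 are as in Table 4. Rises below 30 msec show as None here; see Table 113 and Figure 37. An ECG AE reported as Grade 1 keeps that grade in the AE tables and may show as None in Table 109.

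3. At the QTcF row of SAP Table 4, add a cross-reference to that footnote.
4. Record the change in SAP Section 15, which at present lists none.

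The cost is one query, one footnote on two displays, one cross-reference and one line. No new data are needed, and the AE scale, halting criteria and clinical management stay as they are. The drawback is that, until the wording is reconciled, these two displays differ from Appendix C and an ECG AE reported as Grade 1 could appear as None in Table 109; the footnote discloses this.

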APPENDIX D: BLOOD VOLUME WITHDRAWN DURING THE TRIAL

Laboratory Samples and Estimated Total Blood Volume (mL)

| Study visit | SCREENING | CHECK- IN | INPATIENT PERIOD | | | | FINAL | Total volume | Early term visit |
|--|-----------|--------------|------------------|----|----|-----|--------|--------------|------------------|
| Study Day | -21 to -2 | -1 | 1 | 2 | 3 | 4 | 8 (±2) | | |
| HEMATOLOGY ¹ | 4 | 4 | | | | 4 | | 12 | 4 |
| CHEMISTRY and serum β-HCG, FSH, HIV, HBsAg, HCV ¹ | 5 | 5 | | | | 5 | | 15 | 5 |
| PK ² | | | 54 | 12 | 6 | 6 | | 78 | 6 |
| Total volume/visit | 9 | 9 | 54 | 12 | 6 | 15 | 0 | - | 15 |
| Cumulative total volume | 9 | 18 | 72 | 84 | 90 | 105 | 105 | 105 | |

¹ Clinical blood tests are drawn at Screening Visit, on Day-1, and on Day 4, or ET.

² PK serum samples are drawn on Day 1: 30 min before dosing and at 0.5, 1, 2, 3, 4, 6, 8, 12, 24, 36, 48 and 72 h after dosing, or ET.

1. PREFACE

DMID protocol 16-0118 is a Phase 1 study of zoliflodacin in healthy male and female subjects. The pharmacokinetics (PK)-related objectives of the study are:

- To evaluate the plasma PK of zoliflodacin after administration of a single 4 g oral dose under fasting conditions

This document reiterates key PK elements in the study design of DMID Protocol 16-0118 and thoroughly describes the presentations and summaries of PK data as well as the noncompartmental analysis (NCA) to be included in the PK Report and summarized in the clinical study report (CSR) for this protocol. Shells and mockups are given for all PK-related tables, figures, and listings planned for inclusion in the CSR and/or PK Report. At minimum, mean PK plots as well as listings and summaries of zoliflodacin concentrations and PK parameters will be included in the CSR, while all tables, figures, and listings described in this document will be included in the PK Report.

2. CLINICAL STUDY METHODS

2.1. Analysis Groups

This is a Phase 1, open-label clinical trial of a single 4 g oral dose of zoliflodacin after an overnight fast. Eight healthy subjects who consent to participate in the trial and meet the eligibility criteria will be enrolled into a single cohort. Stratification will not be used in this study. All subjects will be analyzed in a single analysis group and no comparisons will be performed.

2.2. Dose Administration

Eligible subjects will receive a single 4 g dose (2 sachets of 2 g of zoliflodacin reconstituted on the same day and administered in a total of [REDACTED]) orally after an overnight fast. The dose will be administered in a standardized cup. After the [REDACTED] of zoliflodacin is administered, an additional [REDACTED] will be added to the same cup and consumed by the subject to chase the initial dose. Both doses will be completed within a total of 5 min. After dosing, subjects will continue to fast for an additional 4 h while water is allowed *ad lib*.

